Administration of intrathecal lipophilic opioid alone (fentanyl or sufentanil) has been shown to result in sufficient analgesia in the early phase of the labour without causing motor block of the lower limbs or drop of blood pressure due to blockade of the sympathetic neural system (4,5). This method is used routinely in our hospital with a spinal fentanyl dose of 25 micrograms. Until May 2013 our hospital routinely used sufentanil at a dose of 5 micrograms. Alternative option for the spinal opioid would be normal epidural analgesia where the local anesthetic dose is ropivacaine 20 mg and fentanyl 100 micrograms. The fentanyl dose of 100 micrograms could be replaced by sufentanil at a dose of 20 micrograms (6).

Purpose of the study

In this prospective randomized study the efficacy of spinal or epidural opioid (fentanyl or sufentanil) to alleviate the pain during contraction is studied. The opioid is given as a single treatment without any local anesthetics. The primary outcome for the study is the level of analgesia achieved in 20 minutes after the administration of the analgesia. The secondary outcomes are the rate of on-set of the analgesia measured by visual analog scale bar (VAS 0-100 mm; 100 mm worst possible pain; 0 mm no pain) from above 80 mm value (peak during contraction) to under 30 mm value and the duration of the analgesia provided by the neuraxial opioid alone.

Methods

Parturients

A total of 80 primiparous parturients will be recruited (20 parturients in each of the four treatment arms). According to the power calculation we expect to detect a potential difference

of 15 mm in the VAS scores at standard deviation of 15 mm with an 80 % certainty. Potential differences of less than 15 mm are not considered clinically relevant.

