For safety reasons the study will be blinded in such a manner that the parturient or the data collector do not know which analgesia is administered. The anesthesiologist providing the analgesia will prepare the sterile table and draw the medications outside the delivery room. The anesthesia chart will show the randomization code of the parturient. The key to the randomization codes is always available in the anesthesia office. Otherwise, the anesthesia report will be filled in a normal manner and the subsequent epidural analgesia boluses will be marked normally in the chart. The parturient is informed about the procedure using standardized phrases, which do not reveal the (spinal or epidural) nature of the analgesia provided for the midwife or the parturient. In both treatment groups an identical Portex epidural catheter remains in the back of the parturient.

Data will be collected after the drug delivery by another anesthesiologist who is blinded regarding the analgesia provided.

Follow up and data acquisition

The on-set of analgesia is monitored during each contraction on a 0-100 mm VAS scale for up to 30 minutes after the analgesia. The maximum achievable analgesia is expected to be achieved within 30 minutes. The fetal heartrate and the parturient's blood pressure is monitored for

30 minutes according to institutional protocol for neuraxial analgesia. Pruritus is the most common side-effect of the neuraxial opioids and it will be monitored by interview at 0, 10, 20 and 30 minutes. The used measurement scale is: 0 = no pruritus; 1 = mild pruritus; 2 = moderate pruritus; 3 =severe pruritus; 4 = unbearable pruritus. Potential nausea and vomiting will be documented at 0, 10, 20 and 30 minutes (for the past 10 minute interval). Also potential changes in the fetal heart rate, potential ob/gyn consultations and actions due to these consultations will be recorded.

Rescue analgesia and subsequent labour analgesia

The parturient can receive additional analgesia through the epidural catheter at the earliest 30 minutes after the spinal or epidural opioid administration. At 30-45 minutes after the intervention the parturient may get 20 mg ropivacaine in 20 ml saline, whereas after 45 minutes a dose of 20 mg of ropivacaine and 50 micrograms of fentanyl in 20 ml can be given.

Data to be collected in the trial

Background information (height, weight, duration of pregnancy)

from primary health care maternity chart

Gestational data (duration of pregnancy)

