from the hospital Obstetrics software

Prior analgesia during delivery

from the hospital Obstetrics software

Pain VAS (0-100 mm) immediately prior to investigational analgesia and for each contraction thereafter for 30 minutes

Interviewed from the parturient

Pruritus and nausea at 0; 10; 20; 30 minutes after the analgesia

Interviewed from the parturient

Timing of the next epidural analgesic dose, cervical dilatation prior to the next epidural dose. Information on the analgesia provided by the epidural dose.

from the hospital Obstetrics software

Time of delivery, mode of delivery (cesarean delivery, vacuum assisted delivery), potential postpartum operations in the operating theatre.

from the hospital Obstetrics software

Fetal heart rate (FHR)

automatically registered into the hospital Milou system

Archival of the collected data, processing of personal information regarding parturients

The collected data will be archived at the Department of Anaesthesiology in a locked cabinet to which only the investigators have access. When the information is transferred into the electronic data file all directly identifying information will be removed (name and date of birth). The

study participants can be subsequently identified by matching case number with the signed consent form. No directly identifying information is saved in the electronic form.

Analysis of the collected data

For statistical analysis the information is transferred into SPSS software, which is used for comparison of the continuous data (background information, pain VAS scores) and categorical data (adverse events such as nausea, pruritus).

The primary outcome is measured in millimeters on a 100 millimeter line and processed as a continuous variable with 0 mm indicating no detectable pain and 100 mm indicating the worst possible pain. Similarly secondary outcome marker, the duration of analgesia, will be recorded in minutes and processed as a continuous variable. The incidence of adverse events will be recorded as presence or absence of certain adverse events (pruritus, nausea) and analyzed as a categorical variable.

Chi-squared test will be used for categorical variables while Kruskal-Wallis test for independent samples is used for comparisons of continuous variables between the treatment arms.

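### Pruritus is graded 0 to 4 at four times, but the plan compares only its presence or absence; consider tabulating the grade and adding one exploratory comparison of it

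*Combined protocol and SAP*

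**What the plan says.** Under Follow up and data acquisition, pruritus is singled out: "Pruritus is the most common side-effect of the neuraxial opioids and it will be monitored by interview at 0, 10, 20 and 30 minutes". The scale is "0 = no pruritus; 1 = mild pruritus; 2 = moderate pruritus; 3 =severe pruritus; 4 = unbearable pruritus". The same section documents nausea and vomiting at the same four times, each entry covering the preceding 10 minutes. Data to be collected in the trial lists "Pruritus and nausea at 0; 10; 20; 30 minutes after the analgesia".

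Analysis of the collected data turns this into a yes/no variable: "The incidence of adverse events will be recorded as presence or absence of certain adverse events (pruritus, nausea) and analyzed as a categorical variable". The tests are assigned as follows: "Chi-squared test will be used for categorical variables while Kruskal-Wallis test for independent samples is used for comparisons of continuous variables".

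Pruritus is not among the named outcomes. Under Purpose of the study the primary outcome is analgesia at 20 minutes. The secondary outcomes are the rate of onset and the duration of analgesia.

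**The concern.** Two things are missing.

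- **The grade is collected but not used.** The plan names no comparison, summary or table of it. A woman with mild itch and one with unbearable itch contribute the same value to the only planned comparison. If most women in every arm itch, the useful question is how badly, and a test on presence cannot answer it. Tolerability bears on how the result would be used, because Ethical considerations presents the trial as informing a possible move from spinal to epidural opioid.
- **Presence is not defined over time.** Nothing says how four ratings become one yes/no value, or whether itch at minute 0 counts. Eligibility rules out opioids only in the 120 minutes before the study analgesia, so itch at minute 0 is possible. The 0-minute nausea entry covers time before the study drug. Two analysts could therefore obtain different incidences from the same records.

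**Working it through.** **Inputs from the documents.** Four arms of 20 (Parturients); a five-level pruritus grade; chi-squared for categorical and Kruskal-Wallis for continuous variables. The plan states no power or expected rate for pruritus, so there is no figure to reproduce. Its power statement (15 mm difference, SD 15 mm, 80%) concerns pain VAS and is not affected.

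**Assumptions.** Two-sided 5% level (the plan states none). Both drugs behave alike within a route. Every grade distribution below is assumed.

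**Step 1: what the planned test can see.** With x_i women itching in arm i and p the pooled proportion, the statistic is X² = Σ(x_i − 20p)² / [20p(1 − p)], on 3 degrees of freedom. It depends only on the x_i. If incidence is equal across arms, its rejection rate is its false-positive rate, whatever the grades among the women who itch. This step needs no assumed grade mix.

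**Step 2: power by simulation.** 20,000 trials per scenario (simulation standard error at most √(0.25/20,000) = 0.004). The grade columns give % at grades 0/1/2/3/4. A = chi-squared on presence (planned); B = tie-corrected Kruskal-Wallis on worst grade; C = chi-squared on grade 2 or higher.

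| Scenario | Spinal | Epidural | A | B | C |
|---|---|---|---|---|---|
| Severity only, 30% itch | 70/5/12/10/3 | 70/22/6/2/0 | 0.052 | 0.065 | 0.350 |
| Severity only, 50% | 50/10/20/15/5 | 50/35/12/3/0 | 0.045 | 0.141 | 0.551 |
| Severity only, 80% | 20/20/30/22/8 | 20/45/25/8/2 | 0.047 | 0.346 | 0.440 |
| Severity only, 80%, larger gap | 20/15/30/25/10 | 20/50/20/8/2 | 0.047 | 0.565 | 0.764 |
| Severity only, 90% | 10/15/35/30/10 | 10/45/30/13/2 | 0.039 | 0.638 | 0.631 |
| Both rise, 30 v 10% | 70/17/8/4/1 | 90/6/2.5/1.2/0.3 | 0.435 | 0.424 | 0.163 |
| Both rise, 50 v 20% | 50/25/15/8/2 | 80/12/5/2.5/0.5 | 0.663 | 0.666 | 0.356 |
| Both rise, 80 v 40% | 20/30/27/18/5 | 60/22/11/6/1 | 0.899 | 0.921 | 0.738 |
| Both rise, 80 v 60% | 20/30/27/18/5 | 40/30/18/10/2 | 0.344 | 0.410 | 0.304 |
| Both rise, 90 v 80% | 10/30/35/20/5 | 20/50/20/10/0 | 0.139 | 0.606 | 0.613 |
| Incidence only, 90 v 80% | 10/45/27/13.5/4.5 | 20/40/24/12/4 | 0.139 | 0.088 | 0.062 |
| Incidence only, 80 v 60% | 20/40/24/12/4 | 40/30/18/9/3 | 0.336 | 0.229 | 0.104 |
| Extra itch all mild, 60 v 30% | 40/42/12/5/1 | 70/12/12/5/1 | 0.608 | 0.389 | 0.047 |
| Extra itch all mild, 90 v 60% | 10/60/20/8/2 | 40/30/20/8/2 | 0.771 | 0.274 | 0.052 |

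In the first three rows where both rise, adding B to A lifts the chance of any significant result only to 0.449, 0.697 and 0.944. The gains are 0.014, 0.034 and 0.045.

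**Step 3: sensitivity to the assumed mixes.** A separate set of mixes (4,000 trials each) gave, as A v B:

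- severity only: 4% v 40% and 4% v 90% at 90% incidence, 5% v 42% at 70%, 5% v 14% at 50%;
- both rise: 44% v 81% (90 v 70%) and 67% v 87% (80 v 50%);
- incidence only: 95% v 82% (90 v 50%).

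The direction is the same, but the size of the gain varies widely.

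**Step 4: false positives when all arms are alike.**

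| Incidence | A alone | A or B | A or C |
|---|---|---|---|
| 20% | 0.047 | 0.051 | 0.079 |
| 50% | 0.050 | 0.065 | 0.090 |
| 80% | 0.045 | 0.078 | 0.087 |
| 90% | 0.042 | 0.083 | 0.087 |

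**The case against.** **Little is at stake.** Pruritus is neither primary nor a named secondary outcome, no power is claimed for it, and the incidence test is valid. This stands, and it limits the point to an optional improvement.

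**The benefit is assumed.** The clear advantage of a grade test needs equal incidence and a large severity gap. In the scenarios at 80% incidence, grade 2 or higher among itching women is 75% v 44% (60/80 v 35/80) or 81% v 38% (65/80 v 30/80). At 90% it is 83% v 50% (75/90 v 45/90). Nothing in the documents makes this likely. That also stands. What needs no assumption is that the planned test cannot respond to severity at all.

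**Kruskal-Wallis is not the best choice for severity alone.** Chi-squared on grade 2 or higher beats it in four of the five severity-only rows and matches it in the fifth. It is, however, blind to extra mild itch (0.047 and 0.052). Either is defensible if named in advance.

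**The plan might already cover the grade**, since it lists pruritus as categorical and assigns chi-squared to such variables. A chi-squared test on all five grades would have power 0.34-0.68 in the severity-only scenarios, with sparse cells. But the sentence that describes the analysis variable reduces it to presence or absence, so nothing commits the investigators to a grade analysis or table.

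**Stronger readings.** A reader might infer that the two sections contradict each other on how pruritus is recorded. They can be reconciled, because presence follows from the grade (0 v 1-4). A reader might also infer that chi-squared is the wrong test and should be replaced. The incidence-only and mild-itch rows show otherwise: there the planned test is the better one.

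**Conclusion.** The point holds as a cheap improvement to consider. The plan collects a five-level grade for the side-effect it calls the most common and makes no stated use of it. It also leaves presence undefined over the four times. Neither observation depends on any assumed rate.

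The size of the gain does depend on assumptions: 20 per arm, two-sided 5%, drugs alike within a route, and invented grade mixes. For a severity-only difference the planned test rejects at about 4-5%. Kruskal-Wallis on worst grade reaches about 0.07 to 0.64 as incidence goes from 30% to 90%, and chi-squared on grade 2 or higher reaches 0.35-0.76. The gain can be negligible when incidence and severity move together. Neither grade test can stand in for the incidence test.

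**What to change.** Keep the chi-squared incidence test and replace the adverse-event sentence in Analysis of the collected data with, for example:

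> Incidence of pruritus (any grade 1 or higher) and of nausea and vomiting, each at 10, 20 or 30 minutes, is compared between the four arms by chi-squared test; 0-minute records are baseline and are not events. The number of women at each worst pruritus grade (10-30 minutes) is tabulated per arm, and worst grade is compared between arms by Kruskal-Wallis test as an exploratory analysis.

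Chi-squared on grade 2 or higher is an acceptable alternative for the exploratory test; name one before the data are seen. The plan should also say how a woman whose itch at minute 0 persists to minute 10 is counted. The window fits the protocol: "The parturient can receive additional analgesia through the epidural catheter at the earliest 30 minutes after the spinal or epidural opioid administration".

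**Cost.** Two or three sentences; no new data, no change to sample size or primary analysis. Kruskal-Wallis has to be extended beyond continuous variables. One extra test raises the chance of at least one false positive for pruritus from about 4-5% to about 5-8% (8-9% with the grade 2 or higher test), hence the exploratory label. The table alone carries no such cost and is worth having even if the extra test is declined.

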The parturients are ensured not to have any contraindications for spinal/epidural analgesia and they have not received any opioid analgesics by any route within 120 minutes prior to analgesia administration. The randomization is performed when the parturient asks for regional pain relief (i.e. spinal fentanyl according to the institutional practice). The delivery must be in the early phase marked by cervical dilatation of 5 cm or less at the time of the investigational analgesia and the pain VAS during contraction on the 0-100 mm VAS scale shall be at 80 mm or more. The BMI of the parturient at the date of delivery must be 20-35, the pregnancy singleton and the parturient may not have allergy for fentanyl, sufentanil or lidocaine. Furthermore, the parturient's ability to read and speak [Finnish](#) must be adequate so that she can understand the study and she can be interviewed according to the protocol after the analgesia.

The parturient will be given the study brochure prior to painful contractions reach the randomization level (VAS 80 mm). If the parturient agrees to participate in the study and fulfills the inclusion criteria, she will be randomized in to one of the four treatment arms.

Interventions

According to the randomization (20 parturients per group) the parturient is randomized to receive either fentanyl 20 micrograms intrathecally, fentanyl 100 micrograms epidurally, sufentanil 5 micrograms intrathecally or sufentanil 20 micrograms epidurally. The intrathecal medications are diluted according to the institutional protocol into the total volume of 2 ml and epidural medication is diluted into 5 ml volume by sterile saline.

Epidural analgesia is given through the epidural catheter and in all cases epidural catheter is flushed with 2 ml of saline at the end of procedure. The neuraxial analgesia procedure is performed according to the institutional protocol using Portex combined spinal epidural (CSE) set but for epidural drug administration the spinal needle is not used. In both intrathecal (spinal) and epidural medication groups, an epidural G18 catheter is left in the lumbar epidural space.

Blinding

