The fetal heartrate (CTG) recordings will be retroactively analyzed by an obstetrician for potential pathology prior to analgesia and for 30 minutes thereafter. The obstetrician is blinded regarding the intervention.

All data and events are analyzed according to original allocation into respective intervention groups.

Completion of the study

Recruiting of the parturients will begin once the required permits have been received. The parturients will be recruited during 2016 and the results of the study will be published in a peer reviewed journal thereafter. The study will be completed at Helsinki University Central Hospital /Katiolopisto delivery hospital without external sponsors or funding as part of normal quality improvement work.

Ethical considerations

The parturients will be recruited for the study at the very early phase of the labour. The institutional normal protocol is to give 25 micrograms of fentanyl intrathecally. The fentanyl dose used in this study (20 micrograms) does not differ in terms of efficacy from the 25 microgram dose and the efficacy of the other interventions is expected to be in the similar range. Epidural delivery of fentanyl or sufentanil alone without local anesthetic has not been previously studied in the early phase of the labour.

This study will provide information regarding possible replacement of spinal opioid administration with epidural opioid thus avoiding risks and limitations associated with spinal opioid delivery.

No placebo control is used in this study and the parturients will not be exposed to additional injections or painful maneuvers. It is possible that epidural analgesia does not have as fast on-set as spinal analgesia. The only viable option for spinal drug administration currently would be

epidural analgesia which is not routinely preferred at such early phase of the delivery. Therefore, the participating parturients are expected to receive at least as good labour analgesia as those parturients who do not participate in the trial.

References

2. Jenkins JG. Some immediate serious complications of obstetric analgesia and anaesthesia: a prospective study of 145.550 epidurals. *Int J Obstet Anesth* 2005; 14: 37-42.

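### The only analysis named for the primary 20-minute VAS is an omnibus Kruskal-Wallis test over four arms that cross drug with route, so its result neither separates route from drug nor gives an interval to set against 15 mm

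*Combined protocol and SAP*

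**What the plan says.** Purpose of the study: "The primary outcome for the study is the level of analgesia achieved in 20 minutes after the administration of the analgesia". The aim names both factors without ranking them: "the efficacy of spinal or epidural opioid (fentanyl or sufentanil) to alleviate the pain during contraction is studied".

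Interventions: the four arms, 20 women each, are "fentanyl 20 micrograms intrathecally, fentanyl 100 micrograms epidurally, sufentanil 5 micrograms intrathecally or sufentanil 20 micrograms epidurally". This is a two-by-two layout of drug and route, with a different dose for each route.

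Parturients: the sample size rests on 15 mm, SD 15 mm and 80% power. It begins "According to the power calculation we expect to detect a potential difference" and does not say between which arms. It adds: "Potential differences of less than 15 mm are not considered clinically relevant".

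Analysis of the collected data: the primary VAS is treated as continuous, in mm. For continuous variables the section says "Kruskal-Wallis test for independent samples is used for comparisons of continuous variables between the treatment arms". The chi-squared test is reserved for categorical variables.

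Ethical considerations: "This study will provide information regarding possible replacement of spinal opioid administration with epidural opioid".

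No section available for review names a primary contrast, a pairwise or factorial follow-up, an alpha, a multiplicity rule, an effect estimate or a confidence interval.

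**The concern.** The plan raises a question about route (may epidural opioid take the place of spinal?) and one about size (is any difference as large as 15 mm?). Its one named analysis of the primary outcome is a global test that four distributions are equal. If it is significant, the reader does not learn which arms differ or whether the cause is route or drug. If it is not, the reader has a p-value and nothing in mm, and could take the lack of significance as support for replacement. As no follow-up comparison is written down, any comparison then offered as the answer could have been chosen after the results were known. Four arms give six pairs, besides the two main effects.

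**Working it through.** **Inputs.** 20 per arm, difference 15 mm, SD 15 mm and power 80% come from the Parturients section. Alpha is not stated; two-sided 0.05 is assumed. Errors are taken as normal, and SD 20 mm is shown as a less favourable case. Arm order below: fentanyl intrathecal, fentanyl epidural, sufentanil intrathecal, sufentanil epidural.

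**1. The plan's own figure.** For two groups, n per arm = 2(z₁₋α/₂ + z₀.₈₀)²(SD/difference)².
- Alpha 0.05: 2(1.960 + 0.842)²(15/15)² = 15.7, so 16 (17 with the t distribution). With 20 per arm, power is 88.5% (86.9% by t).
- Alpha 0.025: 2(2.241 + 0.842)² = 19.01, so 20.
- Dropout allowances also reach 20: 16/(1 − 0.20) = 20 and 17/(1 − 0.15) = 20.

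None of these routes is documented, so 20 cannot be tied to one calculation. It is not too small for a single pairwise contrast at 0.05. The inputs are those of a two-group comparison, while the named test compares four groups.

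**2. What a significant Kruskal-Wallis result says.** The statistic uses only the arms' rank sums and does not change when arm labels are exchanged. A route effect, a drug effect and a crossover of the same size are each two arms against two, so they must give the same power. Simulated rejection rates (40,000 runs per scenario):

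| Arm means (mm) | Meaning | SD 15 | SD 20 |
|---|---|---|---|
| 0, 15, 0, 15 | route only | 95.9% | 76.7% |
| 0, 0, 15, 15 | drug only | 95.8% | 76.6% |
| 0, 15, 15, 0 | crossover | 95.9% | 76.2% |
| 0, 15, 0, 0 | one arm differs | 87.9% | 61.7% |
| 0, 0, 0, 0 | no difference | 4.7% | 4.8% |

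Under the drug-only pattern at SD 15, at least one of two within-drug route tests at 0.025 rejects in only 5.1%. Those tests separate what the omnibus test does not.

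**3. What a non-significant result says.** With all arms truly equal and Kruskal-Wallis non-significant, at least one within-drug 97.5% interval (epidural minus intrathecal) still has its upper limit at or above 15 mm in 33% of trials at SD 15 and 70% at SD 20. Non-significance therefore does not show that 15 mm is excluded.

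**4. Precision of the missing contrasts** (pooled variance, 76 df).
- Within drug, 97.5%: t₀.₉₈₇₅ × SD × √(2/20) = 2.287 × 15 × 0.3162 = 10.8 mm; at SD 20, 14.5 mm.
- Within drug, 95%: 1.992 × 15 × 0.3162 = 9.4 mm.
- Route pooled over drugs, 95%: 1.992 × 15 × √(1/20) = 6.7 mm.
- Rank-based (Hodges-Lehmann with exact Wilcoxon interval, 97.55%, 20 v 20, simulated): 11.3 mm at SD 15.

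Power of the rank test for 15 mm at SD 15 is 76% under normal errors, against 79% for the separate-variance t-test. Under assumed right-skewed (gamma) data it is 82-90%, against 79%.

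**5. Which contrast should lead** (SD 15; within-drug and pooled figures t-based).

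| Pattern | At least one within-drug test, 0.025 each | Kruskal-Wallis | Pooled route, 0.05 |
|---|---|---|---|
| 15 mm route effect in both drugs | 96% (both reject: 65%) | 96% | 99% |
| 10 mm route effect in both drugs | 68% | 66% | 84% |
| one arm differs by 15 mm | 81% | 88% | 60% |
| means 0, 7.5, 7.5, 15 | 42% | 70% | 60% |

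No contrast is best throughout. Power for a 15 mm interaction is about 60% at SD 15 and 38% at SD 20.

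**The case against.** The aim names route and drug on equal terms and states no directional or non-inferiority hypothesis, and a global test over four arms fits that symmetric aim. The sentence about replacement stands in the ethics section and promises only information. The outcome is recorded in mm, so nothing prevents the investigators from reporting differences. The two-group sample-size inputs suggest that pairwise comparisons were intended. The opening part of the document was not available for review.

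Much of this stands, and it limits the point. A reader might infer that the trial cannot answer its question. The documents do not support that: the design yields the data needed, and what is missing is a written commitment to a contrast and an interval. A reader might also infer that route within each drug is the only proper primary comparison. That does not follow either, since the aim gives route no priority and the pooled route contrast is more powerful when the effect is the same in both drugs.

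The objection does not remove the gap. An implied pairwise intention names no pair and no error rate. The purpose, sample-size and analysis sections were all available, and none of them fills it.

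**Conclusion.** The concern holds as a gap in the analysis plan that should be fixed. Followed as written, the plan yields one p-value for the primary outcome. At SD 15 mm that test rejects in about 96% of trials whether a 15 mm effect belongs to route, to drug or to their crossover (76-77% at SD 20). A non-significant result comes with no interval to compare with 15 mm. By itself, therefore, the result does not directly inform replacement of spinal by epidural opioid.

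The figures assume two-sided alpha 0.05, normal errors and 20 analysed women per arm. That the result does not separate route from drug does not depend on those assumptions; it follows from the form of the test.

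Two stronger conclusions might be drawn and are not supported. Kruskal-Wallis is not an invalid test here, and 20 per arm is not shown to be wrong. Nor do the documents call 15 mm a non-inferiority margin, so the intervals should not be treated as a test against one.

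**What to change.** Before unblinded data are seen, add a paragraph to the analysis section that does the following.

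- Gives the epidural-minus-intrathecal comparison of the 20-minute VAS within each drug, by Wilcoxon test with Hodges-Lehmann difference and interval in mm. This keeps the plan's rank approach, with no data-driven switch of method.
- Controls multiplicity across the two comparisons, for example 0.025 each with 97.5% intervals.
- Reads the intervals descriptively against 15 mm.
- Reports the pooled route difference, the drug difference and the interaction as well.
- Keeps Kruskal-Wallis as the overall test, but not as a gatekeeper to the contrasts.
- States which contrast is primary. The within-drug pair and the pooled route contrast are both defensible; the sponsor should choose in advance.

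It needs no new patients or data. The costs are these:

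- Adjusted intervals are wider (10.8 against 9.4 mm at SD 15, t-based), and at SD 20 the half-width of 14.5 mm may leave the 15 mm question open.
- Power is below that of Kruskal-Wallis for some patterns, such as 81% against 88% and 42% against 70% above.
- The two drugs may disagree: with 15 mm in both, both tests reject in only about 65% of trials, so the plan should say how such a result will be described.
- A non-significant interaction would not justify showing the pooled estimate alone.
- Dose changes with route, so each contrast is route with its own dose, and the report should say so.

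### The trial is meant to inform replacing spinal by epidural opioid, but its primary outcome gets only a four-arm difference test, with no route estimate, no interval and no use of the 15 mm relevance limit

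*Combined protocol and SAP*

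**What the plan says.** - **Use of the trial** (Ethical considerations): "This study will provide information regarding possible replacement of spinal opioid administration with epidural opioid". The stated gain is avoiding the risks and limits of spinal delivery, not better pain relief.
- **Expected result** (Ethical considerations): after comparing two intrathecal fentanyl doses, the text says "the efficacy of the other interventions is expected to be in the similar range".
- **Primary outcome** (Purpose of the study): "The primary outcome for the study is the level of analgesia achieved in 20 minutes after the administration of the analgesia".
- **Sample size** (Methods, Parturients): "A total of 80 primiparous parturients will be recruited (20 parturients in each of the four treatment arms"). The hypothesis behind it is one of difference: "According to the power calculation we expect to detect a potential difference". Its inputs are a 15 mm difference, an SD of 15 mm and 80% power. The next sentence reads "Potential differences of less than 15 mm are not considered clinically relevant".
- **Analysis** (Analysis of the collected data): "Kruskal-Wallis test for independent samples is used for comparisons of continuous variables between the treatment arms".

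The document gives no significance level, no spinal-epidural contrast, no effect estimate or confidence interval, no margin, and no rule for reading a non-significant result. The 15 mm limit does not appear in the analysis section.

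**The concern.** If the reason to switch route is to avoid spinal risks, the pain question is whether epidural opioid is worse by an amount that matters. A four-arm Kruskal-Wallis test asks something else: whether the four distributions are the same. It gives a p-value, with no direction, size or precision for the route effect.

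This matters in two ways. Under the result that the protocol expects, similar arms, the planned output is p > 0.05, which cannot separate similar from undetected. If the test is significant, nothing in the analysis says whether the route difference reaches the plan's own threshold of relevance. Either way the planned primary analysis leaves the replacement question open, although the data could answer it.

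**Working it through.** **Inputs.** From Methods, Parturients: 20 per arm, four arms, SD 15 mm, difference and relevance limit 15 mm, power 80%. Assumed: two-sided alpha 0.05, normal data, equal SDs. SDs of 25 and 30 mm are used only as sensitivity assumptions. *Pooled* means two epidural arms against two spinal arms, 40 v 40.

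**1. The plan's own figure.** Two-sample comparison of 15 mm at SD 15 mm, 80% power:
- Normal formula: n = 2(1.96 + 0.84)² × 15²/15² = 15.7, so 16 per arm.
- Exact t-test: 17 per arm (80.7% power); 20 per arm gives 86.9%.
- Rank-test allowance: 17/0.955 gives 18, and 17/0.864 (the lower bound of the efficiency) gives 20.

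The document does not state its method, but 20 per arm is adequate for a pairwise difference on its inputs.

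**2. Smallest observed difference reaching p < 0.05.** This equals t × SD × √(2/n), which is also the half-width of the 95% interval.
- 20 v 20: 2.024 × 15 × √(2/20) = 2.024 × 4.743 = 9.6 mm.
- 40 v 40: 1.991 × 15 × √(2/40) = 1.991 × 3.354 = 6.7 mm.

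Both lie below 15 mm.

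**3. Four-arm Kruskal-Wallis, by simulation, 20 per arm.**

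| True deficit in both epidural arms | SD | Significant |
|---|---|---|
| 10 mm | 15 mm | about 65% |
| 15 mm | 15 mm | about 96% |
| 15 mm | 25 mm (assumed) | about 55% |
| 15 mm | 30 mm (assumed) | about 40% |

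So a deficit that the plan calls irrelevant is usually significant. A relevant one is rarely missed at the plan's SD. Misses of about 45% and 60% need the larger SDs. Clipping the scores to 0-100 mm hardly changes these figures.

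**4. What non-significance leaves open at SD 15 mm.** In a single 20 v 20 comparison, a true 15 mm deficit is non-significant in 1 − 0.869 = 13% of cases. At true deficits of 5 to 10 mm, about 28 to 33% of comparisons are non-significant with an interval that still includes 15 mm. For the pooled 40 v 40 comparison that share is below 0.3%. The data can therefore usually settle the 15 mm question, but only if the pooled interval is computed.

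**5. Using 15 mm as a margin.** The power that the upper 95% limit falls below margin M when the true deficit is d comes from a noncentral t with noncentrality (M − d)/SE:

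| Comparison | M | d | SD | (M − d)/SE | Power |
|---|---|---|---|---|---|
| 40 v 40 | 15 | 0 | 15 | 15/3.354 = 4.47 | 99% |
| 20 v 20 | 15 | 0 | 15 | 15/4.743 = 3.16 | 87% |
| 40 v 40 | 10 | 0 | 15 | 10/3.354 = 2.98 | 84% |
| 20 v 20 | 10 | 0 | 15 | 10/4.743 = 2.11 | 54% |
| 40 v 40 | 15 | 10 | 15 | 5/3.354 = 1.49 | 31% |
| 40 v 40 | 15 | 0 | 25 (assumed) | 15/5.590 = 2.68 | 75% |

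For 80% power at a 10 mm margin within one drug, the normal formula gives 2(1.96 + 0.84)² × 15²/10² = 35.3, so 36 per arm.

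**The case against.** The purpose statement, the power statement and the test are consistent with one another: they describe a four-arm study looking for differences. The replacement sentence stands in the ethics section, and the expectation of similar efficacy is there to justify exposing women to the arms. Neither is a formal hypothesis. Kruskal-Wallis is a legitimate test, and the plan's sentence about differences under 15 mm already gives a careful reader a yardstick. Any test well powered at a threshold will also often be significant below it.

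Much of this stands, and it rules out three stronger readings that a reader might infer:

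- **That the trial will decide on replacement.** The text promises only information on a possible replacement.
- **That a non-significant result will be taken as support for switching.** No section says so. It is a risk that the plan leaves open. Unless epidural proves better, it is also the only outcome of this analysis that could seem to favour a switch.
- **That a relevant epidural deficit would readily pass unnoticed.** At the plan's SD, a 15 mm deficit in both epidural arms is detected in about 96% of trials. The high miss rates need SDs that no section supports.

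The objection does not remove the gap. The protocol names replacement as the use of its results, and a p-value without a route estimate or interval cannot serve it. The 15 mm yardstick has nothing to be applied to, because no difference in millimetres is planned.

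**Conclusion.** The point holds as a mismatch between stated use and planned analysis, and should be corrected. It does not make the trial invalid or too small. On the plan's SD of 15 mm and an assumed two-sided 5% level, differences well under the relevance limit reach significance, while non-significance says nothing explicit about 15 mm. The percentages rest on normal data with equal SDs. VAS scores after effective analgesia may be skewed towards zero, which would shift the figures but not the logic. Reading 15 mm as a non-inferiority margin is also an assumption: the plan states it as a limit of relevance, and the sponsor has not said that a deficit just under it would be acceptable.

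**What to change.** Keep the Kruskal-Wallis test and add to the analysis section:

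1. The main route analysis is the epidural minus spinal difference in 20-minute VAS, pooled over drugs (40 v 40) and also shown within each drug (20 v 20), with a two-sided 95% confidence interval: t-based, or Hodges-Lehmann if the data are skewed.
2. Epidural opioid is described as not relevantly worse only if the upper limit is below 15 mm, or below a tighter margin that the sponsor sets in advance. Otherwise the interval is reported as it stands.
3. A non-significant Kruskal-Wallis test is not evidence of similarity.

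A mirror rule, calling epidural relevantly worse only if the lower limit exceeds 15 mm, should not be added. At a true 20 mm deficit and SD 15 mm it would succeed in only 31% (40 v 40) or 18% (20 v 20) of trials.

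**Cost.** A few sentences and no more patients, for a 15 mm margin or for 10 mm on the pooled contrast. A 10 mm margin within a single drug would need 36 per arm. Some results must be reported as inconclusive: at a true 10 mm deficit, the pooled upper limit would fail to clear 15 mm in about 69% of trials. The sponsor must also confirm 15 mm as the margin before any results are seen.
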